### Study Enrollment and Withdrawal

Up to 70 males and females (non-childbearing potential), 18-45 years old, inclusive, who are in good health and meet all eligibility criteria, will be enrolled at the University of Iowa. Estimated time to complete enrollment in this study is 17 months.

The target population will reflect the community at large in the Iowa City area. Volunteers will be sought from the University of Iowa VTEU registry of previous participants, web announcements and other mechanisms. Information regarding the study may be provided to the subjects who have previously participated in trials conducted at the participating VTEU sites. Other forms and/or mechanisms of recruitment may also be used.

The University of Iowa IRB will approve all methods of recruitment and recruitment materials prior to use.

The initial responders will be screened by telephone to eliminate those who do not meet inclusion criteria or who have exclusion criteria. Successful candidates will be asked to come to the clinic to further assess their eligibility.

Subject Inclusion and Exclusion Criteria must be assessed by a study clinician licensed to make medical diagnoses and listed on the Form FDA 1572 as the site principal investigator or sub-investigator.

No exemptions are granted on Subject Inclusion/Exclusion Criteria in DMID-sponsored studies. Questions about eligibility should be directed toward the DMID Medical Officer.

## 4.1 Subject Inclusion Criteria

It is the intent of this study to enroll subjects who are considered healthy volunteers. Subjects with pre-existing clinically significant conditions are not considered normal, healthy volunteers. Inclusion criteria must be assessed by a clinician licensed to make medical diagnoses. Subjects must meet all of the following inclusion criteria to participate in this study:

1. Males and females of non-childbearing potential between the ages of 18 and 45 years, inclusive.\*

\*Surgically sterile via tubal ligation, bilateral oophorectomy or hysterectomy or who have been postmenopausal for  $\geq 1$  year confirmed by LH and FSH levels.

2. In good health, as judged by the investigator and determined by vital signs\*

\*Temperature  $< 38^{\circ}\text{C}$ , heart rate  $\leq 100$  bpm and  $> 50$  bpm, systolic blood pressure  $\leq 140$  mmHg and  $> 89$  mmHg, diastolic blood pressure  $\leq 90$  mmHg and  $\geq 60$  mm Hg, medical history and a targeted physical examination. BMI  $\geq 18$  and  $\leq 35$ . Athletically trained subjects with a pulse  $\geq 45$  may be enrolled at the discretion of the principal investigator or designated licensed clinical investigator.

### 3. Acceptable screening laboratories\*

\*Hemoglobin, white blood cell (WBC) count, neutrophil, eosinophil and platelet counts within normal ranges. AST < 44 and ALT < 44 and total bilirubin, creatinine must be equal to or below the upper limit of normal (for eosinophil count, AST, ALT, creatinine, and total bilirubin values below the normal range are acceptable). Random blood glucose must be <140. Urine dipstick testing must be negative for glucose and negative or trace for protein. The following serology tests must be negative: HIV 1/2 antibody, hepatitis B surface antigen (HBsAg), and hepatitis C virus (HCV) antibody. HIV and hepatitis C viral load PCR testing may be performed for individuals suspected of having indeterminate antibody testing.

4. Male participants must be willing to ensure use of condoms and spermicides for 4 months after study drug administration.
5. Provide written informed consent before initiation of any study procedures.
6. Willing to be available for all study-required procedures, and visits for the duration of the study.
7. Able to provide a home phone number, and the name, address, and/or email of a person willing to assist with making contact during the follow-up phase of the study.

## 4.2 Subject Exclusion Criteria

Subjects who meet any of the exclusion criteria at Screening/Baseline will be excluded from study participation. Exclusion criteria must be assessed by a clinician licensed to make medical diagnoses. Subjects will not be able to participate if they have any of the following:

1. History of residing for 6 or more months in regions with endemic cysticercosis as determined by the principal investigator or a designated study physician.
2. Breastfeeding females.
3. Body temperature  $\geq 100.4^{\circ}\text{F}$  ( $\geq 38.0^{\circ}\text{C}$ ) or acute illness within 3 days before administration of study drug (subject may be rescheduled).
4. Chronic or acute medical disorder\*

\*Disorders of the cardiac, pulmonary, liver, kidney, neurologic, gastrointestinal or other system, such that in the opinion of the investigator participation in the study creates additional risk to the subject, or to the validity of the study.

5. Use of chronic systemic medications\*

\*Intermittent use of over the counter medications such as acetaminophen, ibuprofen, cold and sinus medications are permitted for enrollment (please see section 5.6 for instructions on medication use during the study). Topical medications, nasal steroids are permitted throughout the study. Use of prescription medications used less than once per week on average are permitted for enrollment (see section 5.6 for instructions on medication use

during the study). If the subject has taken a short term prescription medication within the past 30 days (e.g. an antibiotic), they should be postponed from enrollment until 30 days have elapsed since the last dose.

6. Has history of sensitivity to related benzimidazole compounds (e.g., albendazole, mebendazole).
7. A diagnosis of schizophrenia, bipolar disease, or history of hospitalization for a psychiatric condition or previous suicide attempt.
8. A history of treatment for any other psychiatric disorder in the past 3 years.\*

\*Past treatment for ADHD does not exclude participants from enrollment as long as the medications have been discontinued for a minimum of 3 months and symptoms are well controlled.

9. Received an experimental agent\* within 1 month before administration of study drug or expect to receive an experimental agent during the 15-day study period.

\*Vaccine, drug, biologic, device, blood product, or medication.

10. Any condition that would, in the opinion of the investigator, place them at an unacceptable risk of injury, render them unable to meet the requirements of the protocol, or that may interfere with successful completion of the study.
11. A history of alcohol consumption\* or any illicit drug use†, or history of substance abuse#. Individuals must agree to abstain from drug or alcohol use for 48 hours prior to enrollment through day 15. .

\*Greater than 7 alcoholic drinks per week. .

†Other than occasional marijuana use (less than once per week for the past 60 days is acceptable).

#Alcohol or illicit drugs within the past 3 years.

12. History of chronic tobacco use in the past 60 days.\*

\*A history of occasional tobacco use (less than 1 pack per week on average) is acceptable. Individuals will be counseled to abstain from use of tobacco and marijuana from screening through day 15.

Vital signs may be performed up to three times to allow for transient conditions to resolve. Screening laboratory values that are abnormal, but are considered to be abnormal due to an acute illness or process may be repeated once. Creatinine, AST, ALT, bilirubin and eosinophil count values that fall below normal values specified in the DMID Toxicity Table are not considered abnormal for the purposes of this study. Additionally, abnormalities in the RBC parameters other than hemoglobin and abnormalities in the WBC differential not specified in the inclusion criteria above (e.g. low basophils or eosinophils) will not be considered exclusionary

for this study and will be followed with the standard safety laboratory follow-up outlined in the study. Laboratory values that are performed as a standard panel by the clinical laboratory, but are not requested for the study, will be reviewed by a licensed study clinician and the clinician will determine whether the laboratory abnormality is clinically significant and should be considered exclusionary. If determined to be clinically insignificant, the study team is not required to follow the laboratory until resolution or the value is determined to be clinically stable.

## **4.3 Treatment Assignment Procedures**

### **4.3.1 Randomization Procedures**

Randomized treatment assignments will be generated by a statistician at The EMMES Corporation, the statistical and data coordinating center (SDCC) for this study. Subjects will be registered using a web-based application developed by The EMMES Corporation. Upon entry of demographic data and confirmation of eligibility for the trial, the subject will be enrolled. After successful enrollment, a treatment assignment number will be displayed on the Enrollment Confirmation screen. The treatment assignment number is referenced against a confidential randomization list provided to designated study personnel on-site to determine the study assignment. The EMMES Corporation will monitor the implementation of this process. Two sentinel subjects in each cohort, one receiving study drug and one receiving placebo, will be dosed and monitored for safety for 48 hours prior to enrolling the remainder of the cohort. As further randomization in the group occurs, these two subjects will be incorporated into the subsequent randomization scheme.

### **4.3.2 Masking Procedures**

This is a double-blinded, placebo controlled trial. Aliquots of 22.5% or 9.6% Synanthic® suspension or placebo solution will be prepared by an unblinded clinical research pharmacist (See Section 6.2, Table 3) and administered orally by a blinded study nurse or investigator using an oral dosing syringe. Immediately following administration of the dose, the subject will drink 100 mL of water to ensure that the entire dose is taken.

### **4.3.3 Reasons for Withdrawal**

Subjects may voluntarily withdraw their consent for study participation at any time and for any reason, without penalty.

Any enrolled subject may withdraw or be withdrawn from the study for the following reasons:

- Medical disease or condition, or any new clinical findings for which continued participation, in the opinion of the site principal investigator or appropriate sub-investigator, would compromise the safety of the subject, or would interfere with the

subject's successful completion of the study, or would interfere with the evaluation of responses.

- Subject no longer meets eligibility criteria.
- As deemed necessary by the site principal investigator or appropriate sub-investigator for noncompliance or other reasons.
- Subject withdrawal of consent.
- Subject lost to follow-up.
- Termination of the study.
- New information becomes available that makes further participation unsafe.

If a subject withdraws or is withdrawn prior to completion of the study, the reason for this decision must be recorded in the case report forms (CRFs). Refer to Section 7.5 for procedures to be followed if a subject withdraws from the study.

#### **4.3.4 Handling of Withdrawals**

The primary reason for withdrawal from the study will be recorded on the Study Status data collection form. Subjects will be encouraged to complete the Early Termination Visit. The Early Termination Visit procedures are listed in Section 7.5. Although subjects are free to withdraw at any time or may be withdrawn by the site principal investigator or appropriate sub-investigator at any time, subjects who receive study drug will be encouraged to remain in the study for follow-up safety assessments and collection of venous blood samples for safety testing. Every attempt will be made to follow all adverse events, including systemic reactions, serious adverse events, ongoing at the time of early withdrawal to resolution.

In the case of subjects who fail to appear for a follow-up safety assessment, extensive effort (i.e., three documented contact attempts via phone calls, e-mails, etc., made on separate occasions and followed by a certified letter) will be made to locate or recall them, or at least to determine their health status. These efforts will be documented in the subject's records.

Subjects who withdraw, or are withdrawn or terminated from the study, or are lost to follow-up after signing the informed consent form, randomization, and receipt of study drug will not be replaced. Unless prohibited by the volunteer, data and samples obtained prior to withdrawal will be included in study analysis. Subjects who withdraw, or are withdrawn or terminated from the study, or are lost to follow-up after signing the informed consent form and randomization but before receipt of study product may be replaced.

#### **4.3.5 Termination of Study**

The NIAID/DMID has the right to terminate this study at any time. Reasons for terminating the study may include, but are not limited to, the following:

- Incidence or severity of AEs indicating a potential health hazard
- Data recording is inaccurate or incomplete
- The Investigator has not been adhering to the protocol or applicable regulatory guidelines in conducting the study

## 5 STUDY INTERVENTION/INVESTIGATIONAL PRODUCT

### 5.1 Study Product Description

#### 5.1.1 Acquisition

Oxfendazole suspension will be purchased through a commercial supplier of the over the counter product.

Oxfendazole placebo solution will be obtained from SRI International. The product was manufactured under cGMP conditions.

#### 5.1.2 Formulation, Packaging, and Labeling

Oxfendazole suspension is currently available as a 9.06% and a 22.5% suspension. Both strengths will be used in this study, as specified in Table 3 (Section 6.2). Dose levels of 0.5, 1, 3, 7.5, 15, 30, and 60 mg/kg will be evaluated sequentially, the dose increasing with each new cohort. Doses will be administered orally using a syringe of a size appropriate to measure the needed volume. A placebo will be prepared by SRI and will also be administered with an oral dosing syringe.

The oxfendazole placebo formulation consists of polyethylene glycol, methyl paraben, and sterile water for injection. These excipients, widely used in pharmaceutical formulations, are NF (National Formulary) or USP (United States Pharmacopeia) grade listed in the FDA's inactive ingredient list. The 15 mL of oxfendazole placebo solution is filled into pre-cleaned 22 mL screw thread vial with 20/400 PTFE (polytetrafluoroethylene) lined cap. Table 2 describes the amount of each excipient in the formulation, container, and closure of oxfendazole placebo.

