## 4 STUDY DESIGN

This Phase I study is a randomized, double-blind, placebo-controlled evaluation of the safety and PK of escalating single oral doses of oxfendazole (0.5, 1, 3, 7.5, 15, 30, 60 mg/kg) in healthy volunteers. The dose will be increased approximately three-fold (one-half log) at each increment, and each cohort will comprise 10 volunteers (8 drug, 2 placebo). Subjects will be monitored for 2 weeks after dosing, including monitoring the PK and metabolism of oxfendazole in blood and urine.

Two sentinel subjects (one randomized to receive study drug and the other to receive placebo) will be dosed and monitored 48 hours for adverse events prior to enrolling the remaining subjects in each cohort. If no drug-related serious adverse event or laboratory grade 3 study drug related events are observed within the 48 hour period, the remainder of the cohort will proceed with dosing. Each new cohort will be dosed only after the 2-week safety data for the preceding group have been analyzed. A Safety Review Committee (SRC) composed of the Protocol Principal Investigator and Independent Safety Monitor will review blinded safety data for the completed cohort. If a clinically significant AE is observed that is possibly drug related, the SRC will determine if an ad hoc SMC meeting should be called. Up to 70 volunteers (56 drug, 14 placebo) will complete the study. The Safety Monitoring Committee (SMC) will review the safety data either when or if the final dose is reached.

For the Phase I study, between 10 and 70 subjects (8:2 drug: placebo in each cohort receiving increasing doses) will be enrolled. This number should be small enough to perform the study safely and efficiently, yet large enough for an estimation of the PK, metabolism, and the identification of any common side effects of oxfendazole.

The study will be conducted on an outpatient basis at the University of Iowa. Screening for subject recruitment will continue throughout the study until the requisite number of volunteers is enrolled. Each subject will be evaluated over a 2 week period. Projected duration of subject participation will be 3-6 weeks of face to face visits, including the screening period. It is anticipated that it will take 18 months to finish the study.

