## 5.2 Dosage, Preparation and Administration of Study Intervention/Investigational Product

**Table 3. Schema for administration of Synanthic® available product strengths**

Dose ID	Synanthic®		Dosing protocol		
	Concentration of dosing suspension (mg/mL)	Source of dosing suspension	Protocol dose (mg/kg)	mL to be administered	Vol for 80 kg subject (mL)
A	90.6	9.06% Synanthic®	0.5	kg x 0.0055	0.44
B			1.0	kg x 0.011	0.88
C			3.0	kg x 0.033	2.65
D			7.5	kg x 0.083	6.62
E	225	22.5% Synanthic®	15	kg x 0.067	5.32
F			30	kg x 0.133	10.66
G			60	kg x 0.267	21.33

Note: Aliquots will be removed from the Synanthic® stock bottle immediately after mixing, as the marketed drug is a suspension. The content of the oral dosing syringe will be mixed in the pharmacy and transported to the clinical research for administration. Administration must occur within 20 minutes after mixing in the pharmacy. Immediately following administration of the dose, the subject will drink 100 mL of water to assure that the entire dose is taken. If the dose is not administered within 20 minutes it should be discarded and a fresh dose mixed in the pharmacy.

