### Statistical Analysis of PK

PK parameters for oxfendazole will be calculated using non-compartmental analysis. Only plasma concentrations greater than the respective lower limits of quantitation (LOQ) for the assay will be used in the PK analysis.

The maximum plasma concentration ( $C_{max}$ ) and time to  $C_{max}$  ( $T_{max}$ ) will be taken from the data description. The elimination rate constant,  $\lambda_z$ , will be calculated as the negative of the slope of the terminal log-linear segment of the plasma concentration-time curve. The range of data to be used for each subject and treatment will be determined by visual inspection of a semi-logarithmic plot of concentration vs. time, but will include at least three plasma concentration-time points. Elimination half-life ( $t_{1/2}$ ) will be calculated according to the following equation:

$$t^{1/2} = \frac{0.693}{\lambda_z}$$

Area under the curve to the final sample with a concentration  $\geq$  LOQ ( $AUC_{0-t}$ ) will be calculated using the linear trapezoidal method and extrapolated to infinity using

$$AUC_{\infty} = AUC_{0-t} + \frac{C_{if}}{\lambda_z}$$

where  $C_{if}$  is the final concentration  $\geq$  LOQ.

Oral clearance ( $CL/F$ ) and volume of distribution ( $V_z/F$ ) will be calculated according to

$$CL/F = \frac{Dose}{AUC_{(0-\infty)}} \quad \text{and} \quad V_z/F = \frac{Dose}{\lambda_z \times AUC_{(0-\infty)}}.$$

All PK calculations and graphs of individual subject data will be done using appropriate computer software, as determined by the sponsor.

Listing of individual subject plasma concentrations, actual blood sampling times, PK parameters, and graphs of concentration vs. time will be prepared by dosing cohort. Plasma concentrations and PK parameters will be summarized by and compared among dosing cohorts using descriptive statistics. The relationship between  $C_{max}$  and  $AUC_{\infty}$  and dose, i.e., dose proportionality, will be examined using the power model, i.e.,

$$P = a \times Dose^b$$

where P represents the parameter and a and b are constants. A value of b of approximately 1 indicates linear PK.

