4.7 Additional Analyses

In order to assess dose proportionality and linearity across the range of administered doses, plots of dose versus exposure ($AUC_{0-\infty}$ or C_{max}) will be presented with corresponding descriptive statistics such as R^2 . Parameter estimates for an appropriate (simple least squares, weighted least squares, or power) regression model will also be provided [2, 3]. Model selection will be guided by graphical diagnostics to assess model fit.

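### The pooled exponent used to judge linear PK partly mixes dose with product strength, because the suspension changes between 7.5 and 15 mg/kg

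*Protocol*

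**What the plan says.** Protocol 5.1.2 plans seven rising doses: "Dose levels of 0.5, 1, 3, 7.5, 15, 30, and 60 mg/kg will be evaluated sequentially, the dose increasing with each new cohort". Two commercial strengths supply them: "Both strengths will be used in this study, as specified in Table 3 (Section 6.2"). The table itself stands in Section 5.2, under the title "Schema for administration of Synanthic® available product strengths". It assigns doses A to D (0.5, 1, 3, 7.5 mg/kg) to "9.06% Synanthic" and doses E to G (15, 30, 60 mg/kg) to "22.5% Synanthic". Under Protocol Section 4, "each cohort will comprise 10 volunteers (8 drug, 2 placebo"), so each dose has eight active subjects.

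Protocol 10.4 relates Cmax and AUC to dose by P = a × Dose^b, with dose as the only regressor, and adds: "A value of b of approximately 1 indicates linear PK". No margin or interval defines approximately.

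SAP 4.7 opens with "In order to assess dose proportionality and linearity across the range of administered doses". It plots dose against exposure, allows a simple, weighted or power regression, and chooses among them by graphical fit. It does not repeat the criterion for b. Neither document has a strength term, a fit within strength, or a caveat about the change of product.

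**The concern.** Strength is fully nested in dose. A single exponent fitted over 0.5 to 60 mg/kg measures dose proportionality alone only if the two suspensions deliver the same fraction of the dose. If they do not, there is a step in exposure at the switch, and part of it is absorbed into b. The error can go either way: linear PK can look non-linear, or a real departure can be offset so that b lands near 1.

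At stake is the wording of a linearity statement over a 120-fold dose range. Protocol 10.3.2 and SAP 4.5 allow group-level PK results to be used for development planning and grant applications, so that statement may travel beyond the trial report.

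**Working it through.** **Inputs from the documents:** seven doses, the strength for each, and eight active subjects per dose. **Assumed, because the documents give no value:** R, the bioavailability of the 22.5% relative to the 9.06% product (0.7 to 1.5), and a between-subject SD of log exposure of 0.4. The fit is taken as least squares of ln(P) on ln(dose in mg/kg).

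**1. Where the switch lies.** Volume for 80 kg = 80 × dose / concentration.
- 7.5 mg/kg: 80 × 7.5 / 90.6 = 6.62 mL (Table 3: 6.62).
- 15 mg/kg: 80 × 15 / 225 = 5.33 mL (Table 3: 5.32).

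The other five volumes also agree within about 0.01 mL. The volume falls while the dose doubles, which confirms the change of product at that point.

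**2. How a product step enters b.** Let s = 0 for doses A to D and 1 for E to G. Then fitted b = true b + λ ln(R), where λ is the slope of s on ln(dose).
- ln(dose): −0.693, 0, 1.099, 2.015, 2.708, 3.401, 4.094. Mean 1.803; sum of squares about the mean 18.646.
- Cross-product with s: (2.708 + 3.401 + 4.094) − 3 × 1.803 = 4.793.
- λ = 4.793 / 18.646 = 0.257.

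**3. Size of the shift when true b = 1.**

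| Assumed R | ln(R) | Shift | Fitted b |
|---|---|---|---|
| 0.7 | −0.357 | −0.092 | 0.91 |
| 0.8 | −0.223 | −0.057 | 0.94 |
| 1.25 | 0.223 | 0.057 | 1.06 |
| 1.5 | 0.405 | 0.104 | 1.10 |

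In the masking direction, a true b of 0.9 is fitted as 1.0 if R = exp(0.1 / 0.257) = 1.48.

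**4. Precision of the pooled b.** SE = 0.4 / √(8 × 18.646) = 0.033; 95% half-width 1.96 × 0.033 = 0.064.

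**5. Exponents within strength.** These do not depend on R.
- 0.5 to 7.5 mg/kg: sum of squares 4.283; SE = 0.4 / √(8 × 4.283) = 0.068; half-width 0.13.
- 15 to 60 mg/kg: sum of squares 0.961; SE = 0.4 / √(8 × 0.961) = 0.144; half-width 0.28.

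**6. One model with a strength term.** The correlation of s with ln(dose) is 0.848, so r² = 0.719.
- SE of b rises by √(1 / (1 − 0.719)) = 1.89, to 0.062.
- SE of the strength coefficient = 0.4 / √(8 × 1.714 × 0.281) = 0.20, where 1.714 = 3 × 4 / 7.
- exp(±1.96 × 0.204) runs from 0.67 to 1.49. An estimated R inside that range cannot be told from 1.

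**7. Do the within-strength exponents separate the two explanations?** Two noise-free cases:

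| Case | Pooled b | b, 0.5–7.5 | b, 15–60 | Strength model |
|---|---|---|---|---|
| Pure product step, R = 0.7 | 0.91 | 1.00 | 1.00 | b 1.00, ratio 0.70 |
| No product difference; exposure proportional to dose / (1 + dose/30) | 0.79 | 0.93 | 0.50 | b 0.85, ratio 0.81 |

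The within-strength exponents tell the cases apart. The strength term, in the second case, relabels part of a true saturation as a product difference.

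**The case against.** The case for leaving the plan alone is substantial.

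- **No evidence of a difference.** Protocol 2.1.1.1 describes both strengths as aqueous suspensions of the same drug from one manufacturer. A reader might infer that the products are absorbed differently, or that a linearity conclusion would be wrong. The documents support neither; R is purely assumed, and at 0.8 or 1.25 the shift of 0.06 is no larger than the pooled half-width. This stands.
- **Exploratory analysis, no decision rule.** A reader might infer that at R = 0.7 the trial would reject linearity, since 0.092 exceeds 0.064. Protocol 10.4 has no confidence-interval rule for b and disclaims formal comparisons between doses. SAP 4.7 does not use the criterion at all and is headed Additional Analyses. The secondary endpoints are reported per dose group and do not depend on b. This stands and limits the weight of the point.
- **Partial confounding.** A reader might infer that dose and product effects are indistinguishable. A step with unchanged slopes differs from a slope that falls within 15 to 60 mg/kg. CL/F by dose group (SAP Exhibit 16) could also show a step, though nothing directs anyone to look for one or to consider product as its cause.
- **The projected active dose.** Protocol 2.1.3.2 mentions 9.49 mg/kg, which lies across the switch. A reader might call inference there extrapolation. It is interpolation between two observed cohorts of eight active subjects each.
- **Practical reason for two strengths.** For 80 kg, 60 mg/kg from the weaker product would take 80 × 60 / 90.6 = 53 mL, and 0.5 mg/kg from the stronger 80 × 0.5 / 225 = 0.18 mL. Using two products is understandable. The point concerns only the analysis.

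**Conclusion.** The point holds in a limited form. The pooled exponent cannot by itself support a linearity statement over 0.5 to 60 mg/kg, because product changes with dose and equal absorption is neither stated nor tested. The possible shift is modest: about 0.06 for R of 0.8 or 1.25, and 0.09 to 0.10 for R of 0.7 or 1.5. These figures rest on assumed values of R, equal cohorts and a log-log fit; the precision figures rest on an assumed SD of 0.4. The confounding is partial, so reporting exponents within each strength recovers most of what can be learned. What remains unresolvable is a step between 7.5 and 15 mg/kg, which can be assigned to dose or product only by assuming a common slope on both sides. This is a cheap improvement to an exploratory analysis, and no ground for doubting the design or the per-dose PK results.

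**What to change.** In SAP 4.7 and Protocol 10.4:

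1. Keep the pooled fit, and also report the exponents with 95% confidence intervals separately for 0.5 to 7.5 mg/kg and 15 to 60 mg/kg.
2. Mark the strength change on the dose-exposure plots.
3. State the limitation on a step between 7.5 and 15 mg/kg, and word any linearity statement across the full range accordingly.
4. Show a model with a strength term, if at all, only as a sensitivity analysis, because of its low power and its tendency to absorb true non-linearity.

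The cost is SAP and protocol wording plus two short regressions, with no new data and no change to dosing or product. The downside is the imprecision of the within-strength exponents, above all the upper one: agreement between them is supportive rather than proof, and the linearity statement will be weaker than one based on the pooled fit alone.
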